mechanisms of insulin resistance, and the development of a non-invasive biomarker in children at an increased risk of developing insulin resistance.

Hypothesis and Specific Aims

We hypothesize that when compared to normal weight or obese insulin sensitive children, obese insulin resistant children will exhibit altered circulating blood cell bioenergetics and a more oxidized plasma redox state and that these alterations will be associated with decreased resting energy expenditure and impaired fatty acid oxidation (FAO). Furthermore, we hypothesize that poor oxidative capacity over time may distinguish between metabolically healthy obese (MHO) and metabolically unhealthy obese (MUO) phenotypes, as well as be predictive of T2D development. We also hypothesize that bioenergetics, REE and FAO will be improved in obese T2D or insulin resistant children after 6 months of metformin therapy that will be prescribed as part of their clinical care. To test these hypotheses, we will evaluate the following Specific Aims:

Specific Aim 1: Determine whether peripheral blood mononuclear cell (PBMC) and platelet bioenergetics (oxidative phosphorylation, glycolysis and fatty acid oxidation) are impaired and whether plasma glutathione-mediated redox/antioxidant capacity is decreased in obese insulin resistant children as compared to normal weight and obese insulin sensitive children.

Specific Aim 2: Determine whether resting energy expenditure (REE) and fatty acid oxidation (FAO) are decreased in obese insulin resistant as compared to lean and obese insulin sensitive children and whether REE and FAO are correlated with bioenergetic and redox profiles.

Specific Aim 3: Determine whether the bioenergetic oxidative capacity measured in circulating cells, PBMCs/platelets, and FAO are valuable predictive markers of T2D in obese children, in addition to distinguishing MUO from MHO subjects.

Specific Aim 4: Determine whether circulating blood cell bioenergetics and whole-body REE and FAO are modulated by metformin therapy that will be prescribed as part of clinical care in

Title: Bioenergetics and Metabolism in Pediatric Populations

PI: [name].

obese children with T2D or insulin resistance.

Study Design and Procedures

This study consists of:

1. An observational cross sectional bioenergetic and metabolic analysis of several groups of children including lean, obese, and T2D.

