At the initial study visit eligible participants will be met by study staff at the designated study location. Participants will arrive after an overnight fast of no food or liquid after 12 am, except for water and medications the day of the visit. The study visit may include collection of anthropometric measurements, tanner stage assessment, physical activity questionnaire, depression scale, resting energy expenditure, body composition by bioelectrical impedance, saliva, buccal swab, blood, stool, and urine collection. Attempts to repeat anthropometric measurements, body composition by bioelectrical impedance, and resting energy expenditure will occur if a reading is not given the first time or if the child is unable to comply during the first measurement. The parent and subject will not have to stay at the research location for the entire

visit in order for the samples to be obtained. Instructions will be given to the parents for collection of samples if the parent and child decide not to remain at the research location for the entire visit.

If a procedure(s) (see below) is not successfully completed, the parent and, if warranted, the participant may be asked to return to the study site for an additional visit to re-attempt the procedure. The decision to ask the parent/participant, to return for another attempt will be made by the principal investigator and/or co-investigator. When a decision is made to re-attempt the procedure, study staff will contact the parent and explain what procedure they would like to re-attempt and if the parent is willing, schedule the visit. If a blood draw or fat oxidation estimation will be re-attempted, the parent will be re-advised that if the parent wishes their child to complete the procedure, the child will need to be fasting including no food or liquid after 12 am, except for water and medications the day of the visit. The study visit will be conducted in the same manner as the initial visit, with only the desired procedure(s) being re-attempted.

The collection of stool, saliva, and buccal swab samples is optional, and these samples may not be collected if the subject or parent does not want the sample(s) to be used for future research.

Study Procedures to be conducted at each visit:

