1. Intake of Food and Liquid: A parent will be asked by the study staff about the food and drink that the subject eats and drinks the day of and day following the visit (up until the last urine sample is collected for fat oxidation estimation). This is important because the diet will influence the fat oxidation estimation.
2. Anthropometrics: Anthropometric measurements including height, weight, waist circumference, blood pressure, and pulse will be obtained using standardized techniques. BMI-for-age will be calculated and plotted on CDC growth charts to confirm lean/obese stratification.
3. Tanner (Puberty) Stage Assessment: Parents will be asked to complete a form with drawings depicting pubertal development. This form will be used to determine pubertal status. A physician may examine the subject for Tanner Stage (if the parent agrees) during the visit in order to confirm the parental report and for purposes of analyzing study results. The questionnaire given to parents to complete is subjective and a parent could potentially incorrectly assess Tanner Stage. While the inclusion/exclusion criteria prevents the inclusion of those with puberty development, if a parent incorrectly assesses his/her child's Tanner Stage, then this may alter the results or may cause the exclusion of many potential participants based on the parents response, especially in obese participants. Because the results from the samples are reliant on the participants being pre-pubertal with no signs of maturation, conclusions may be incorrectly drawn from the study data if a child has pubertal development. At the beginning stages of puberty, insulin levels rise dramatically showing insulin resistance. Thus, if the study determines the child to have insulin resistance but insulin resistance is actually due to development of puberty instead of being MUO then this

could alter the results and conclusions made from the study. Because of this, it is important to the study and the results to have the correct Tanner Stage level for each participant.

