4. Physical Activity Questionnaire (Elementary School): A parent or participant will complete a form indicating the level of physical activity the participant had during the previous week in order to provide general estimates of physical activity levels for each subject during a 7-day period prior to the study. In addition, the parent or participant will be asked about the participant's physical activity from the previous months leading up to the study visit.
5. Depression Scale: With assistance from the parent, a child will complete a form (Center for Epidemiological Studies Depression Scale for Children (CES-DC)) used as a depression scale. This scale will be used to account for depression as a confounding factor that could affect oxidative and bioenergetics parameters.
6. Saliva and Cheek Cells: We will ask each participant if he/she is willing to provide a sample of saliva and have his/her buccal mucosa swabbed. Cheek cells will be collected by study staff using a soft swab to gently swipe the inside of the child's cheek bilaterally for approximately one minute each, per cheek. The swabs and saliva will be labeled with the study ID number of the participant and the study acronym. These samples will remain on ice or in a refrigerator until transported to the PI's laboratory. After the sample has been processed, the sample will be stored at -80°C in the PI's laboratory. This sample will be used for future research studies on pediatric nutrition and may be retained until it is used up. This is optional and is not a requirement for completion of the study visit.
7. Blood Collection: A pediatric nurse or trained phlebotomist will collect blood from the participant under fasted conditions. Depending on the child's weight, up to the maximum allowed per the guidelines provided by Arkansas Children's for the maximum allowable single blood draw volumes will be collected. The volumes are derived using a conservative 3.0 ml/kg estimate as well as a 5% of total body volume estimate. Numbing cream or a pain relieving device (Buzzy) may be used for the blood draw. Blood samples may be used for:

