11. Body composition may be assessed by bioelectrical impedance analysis using the Tanita Body Composition Analyzer. A device (InBody 570 Body Composition

Analyzer) similar to the Tanita, is routinely used in the clinic. The Tanita requires participants to stand still with bare feet on the weighing platform while a small amount of electrical current is used to measure impedance.

12. Resting energy expenditure by indirect calorimetry: A metabolic cart (Microlife Medgem Analyzer may be used to make gas exchange measurements (i.e. volume of oxygen consumed and volume of carbon dioxide produced by the participant). Measurements will be performed in a quiet, temperature-monitored room. Children will be required to lie still without falling asleep for the duration of the measurement. The data obtained will be used to assess whole-body substrate oxidation rates.

Participants in the obese insulin-resistant and newly prescribed metformin groups may be asked to participate in additional visits. The additional study visits will include the same procedures as the initial visit. For the newly prescribed metformin group, participants/parents will be asked to verify their compliance with metformin by bringing their medication to the visit to show study staff and asking the parent/participant to report their compliance. In addition, if a procedure(s) is not successfully completed, the parent and, if warranted, the participant may be asked to return to the study site for an additional visit to re-attempt the procedure. The decision to re-attempt the procedure(s) will be made by the principal investigator and/or co-investigator and the same steps as described for the re-attempt of a procedure from the initial visit followed.

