Study investigators, research staff, or any qualified personnel will conduct recruitment of study participants using IRB approved advertisement. Advertisements may be distributed in the form of postcards or flyers via direct mail or to various locations, including pediatricians' offices, health fairs, daycare centers, schools/universities, recreational centers, child retail stores, websites (ACH, ACRI, ACNC, UAMS, and others as applicable) and churches. Also, print or digital ads may appear in newspapers, magazines, social media and circulars. On-hold phone messages, BoomText messages, screensavers, and radio/television advertisements may be used. In addition, research staff may contact parents who expressed an interest in our studies or who previously agreed to be contacted regarding future studies. The research staff will educate the parents and children about the study. We will also work with physicians at ACH to identify subjects that may qualify. They will provide study staff with contact information for the patient, and study staff will call and educate the parents and children about the study. The physicians will introduce the study to their patients; if the patient is interested the physician will obtain contact information so that the study staff can follow up and talk to the parents and children about the study. In this case, the only contact by study staff would be to introduce the study followed by informed consent in person. We will protect all personal information obtained during recruitment, enrollment, and testing processes, and maintain this in a locked drawer or cabinet.

175 pre-pubescent children ages 5-9 years old or T2D/insulin resistant children ages 5-17 years old who have been newly prescribed metformin will be recruited and may enroll for this study with the goal that 130 subjects stratified across the following groups will complete the study: i) healthy lean (n=20); ii) healthy obese (n=20); iii) obese insulin resistant (n=70); obese with new

Title: Bioenergetics and Metabolism in Pediatric Populations

PI: [name].

metformin prescription(n=20) (children with T2D or insulin resistant who have been newly prescribed metformin therapy as part of their clinical care). Every attempt will be made to ensure that groups are balanced with respect to sex and ethnicity.

Inclusion Criteria:

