At the time of collection, samples will be kept on ice or refrigerated (with the exception of stool which will be kept in a freezer) in the pediatric clinical research unit or in [name] laboratory (Rm 4015 of ACRI) until they can be transported to the research laboratory. Samples will be kept at -80°C once the initial processing and analyses have taken place. Samples will be stored in Room N2002 Freezer N2002FT6 or N2002FT18 of ACRI in [name] laboratory. These are monitored continuously for proper temperature and working condition. None of a subject's personal identifiers will be present on any biological sample, except the unique subject ID and the study acronym. The samples may be used until they are used up for research on pediatric nutrition.

At any time if the subject decides that he/she does not want to participate anymore, that subject's data will be included as part of the planned analysis of study data. No more information will be collected after withdrawal, however all data and samples collected prior to withdrawal will still be used.

Information pertaining to this study will be made publically available through the ClinicalTrials.gov website.

Data Analysis

Statistical and Power Analyses: 175 pre-pubertal children ages 5-9 years old will be recruited for this study assuming that 130 subjects stratified across the following groups will complete the study: i) healthy lean (n=20); ii) healthy obese (n=20); iii) obese insulin resistant (n=70); obese

Title: Bioenergetics and Metabolism in Pediatric Populations

PI: [name].

with new metformin prescription (n=20). A one-factor analysis of variance (ANOVA) will be used to compare mean outcome of interest across the groups of children (healthy lean, healthy obese, obese insulin resistant and obese T2D). Pair-wise comparisons using Tukey-Kramer post-hoc tests will be used to identify groups whose means differ significantly while retaining the family-wise error rate at 5%. Outcomes will be also checked to verify that the assumptions of the parametric tests are met. When substantial deviation from assumptions are encountered, and if suitable transformation are not found, groups will be compared using the nonparametric Kruskal-Wallis rank test, followed by Bonferroni corrected Wilcoxon rank-sum tests to identify groups that differ. Generalized linear model (GLM) will also be used to incorporate important covariates and effect modifiers into the analysis.

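### For Aim 2, the stated group comparison of resting energy expenditure ignores body size, and the covariate model the plan also promises is not specified for it or made decisive

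*Combined protocol and SAP*

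**What the plan says.** Specific Aim 2 is directional: "Determine whether resting energy expenditure (REE) and fatty acid oxidation (FAO) are decreased in obese insulin resistant as compared to lean" and obese insulin-sensitive children. It also asks whether REE correlates with the bioenergetic and redox profiles.

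All group outcomes share one generic plan in Data Analysis: "A one-factor analysis of variance (ANOVA) will be used to compare mean outcome of interest across the groups of children", followed by Tukey-Kramer comparisons. If assumptions fail, Kruskal-Wallis and Bonferroni-corrected Wilcoxon tests take over. Neither route has a covariate. The same paragraph then commits to a generalized linear model (GLM) for important covariates and effect modifiers. It does not say which covariates, for which outcomes, or how the GLM ranks against the ANOVA. The Sample Size Justification powers Aims 1 and 2 on the ANOVA, with 110 children in three groups (70 insulin resistant, 20 healthy obese, 20 lean). The ANOVA paragraph lists four groups, the fourth being the metformin/T2D group, with 130 children expected to complete.

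REE is described through "gas exchange measurements (i.e. volume of oxygen consumed and volume of carbon dioxide produced by the participant"), without an analysis unit or scaling. Aim 4 speaks of whole-body REE.

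Body-size data are foreseen. Height, weight and waist are measured, and "Body composition may be assessed by bioelectrical impedance analysis using the Tanita Body Composition Analyzer". For failed readings, "Attempts to repeat anthropometric measurements, body composition by bioelectrical impedance, and resting energy expenditure will occur if a reading is not given" the first time. None of this is linked to the REE analysis. The stated use of BMI-for-age is group assignment: "BMI-for-age will be calculated and plotted on CDC growth charts to confirm lean/obese stratification". The stated balancing aim is "Every attempt will be made to ensure that groups are balanced with respect to sex and ethnicity". The Inclusion Criteria define lean as BMI from the 5th to below the 85th percentile, and obese as the 95th percentile or above.

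**The concern.** Whole-body REE rises with the amount of metabolically active tissue. The lean and obese groups are formed on BMI, so the grouping factor is itself a body-size variable. An unadjusted comparison of insulin-resistant with lean children therefore estimates the metabolic difference plus the REE difference due to size. Aim 2 predicts lower REE in the insulin-resistant group. Size pushes their whole-body REE up, so the bias works against the hypothesis.

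A real deficit relative to lean controls could be missed, or reported as a significant excess. If the ANOVA and the GLM disagree, nothing says which one answers Aim 2. Pooled correlations of REE with blood-cell and redox measures can carry the same size signal.

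**Working it through.** **The plan's own figure.** The Sample Size Justification gives a minimum detectable Cohen's f of 0.33 (N = 110, three groups, 80% power, alpha 0.05). Using the noncentral F with λ = N·f² and 2 and 107 degrees of freedom, I obtain f = 0.300; at f = 0.33 power is 87.3%. The stated figure is conservative, so the gap does not affect this point. The calculation contains no body-size term.

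**Inputs from the plan.** Insulin resistant 70, lean 20, Tukey at a family-wise 5%.

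**Assumed inputs (none is in the documents).** REE slope b = 15–25 kcal/day per kg of fat-free mass (FFM); insulin-resistant minus lean FFM gap g = 3–8 kg; within-group FFM SD 3.5 kg; residual REE SD 100 kcal/day; true size-adjusted deficit 100 kcal/day.

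**Unadjusted contrast.**
- Expected difference = −100 + b·g. It turns positive once g exceeds 100/b, which is 6.7 kg at b = 15 and 4 kg at b = 25.
- SD = √(100² + (3.5b)²), which is 112.9, 122.1 and 132.9 for b = 15, 20 and 25.
- SE = SD·√(1/70 + 1/20) = SD × 0.2535.
- Tukey critical value 2.377 (three groups, df 107).

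**FFM-adjusted contrast.**
- SE = 100·√(1/70 + 1/20 + g²/(107 × 3.5²)), which is 26.7, 28.9 and 33.6 at g = 3, 5 and 8. The expected difference is −100 whatever the slope, and df is 104.

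Probabilities from the noncentral t, three groups, N = 110:

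| Slope b | Gap g (kg) | Expected unadjusted difference | Declared lower, unadjusted | Declared higher, unadjusted | Declared lower, FFM-adjusted |
|---|---|---|---|---|---|
| 15 | 3 | −55 | 33% | 0% | 91% |
| 15 | 5 | −25 | 7% | 0% | 86% |
| 15 | 8 | +20 | 0% | 5% | 72% |
| 20 | 3 | −40 | 14% | 0% | 91% |
| 20 | 5 | 0 | 1% | 1% | 86% |
| 20 | 8 | +60 | 0% | 33% | 72% |
| 25 | 3 | −25 | 5% | 0% | 91% |
| 25 | 5 | +25 | 0% | 5% | 86% |
| 25 | 8 | +100 | 0% | 72% | 72% |

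**Four groups, as the ANOVA paragraph lists them.** With N = 130 and df 126 the critical value is 2.604. Declared lower becomes 0–25% unadjusted and 68–88% FFM-adjusted; wrong-direction significance at 8 kg becomes 3–64%. This gives the fourth group the same FFM spread. If its FFM SD were 12 kg (an assumption, as that group reaches 17 years 5 months), the inflated pooled variance would bring the wrong-direction figure down to 1–33%.

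**Sensitivity, three groups.** Residual SD 75–150: declared lower 0–50% unadjusted and 35–99% adjusted, wrong direction at 8 kg 3–85%. True deficit 50–150 (residual SD 100): 0–90% unadjusted, 19–100% adjusted. With no true deficit, the unadjusted contrast declares whole-body REE higher 21–100% of the time.

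**Cross-check on a standardised scale.** Let r be the within-group correlation of REE with size and D the size gap in within-group SDs; the bias is r·D. With a deficit of 0.8 SD, detection is 35% unadjusted and 76% adjusted at r = 0.3, D = 1, and 0.1% and 70% at r = 0.5, D = 2. The conclusion is the same.

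**Insulin resistant versus healthy obese.** If FFM is equal, b·g = 0 and there is no bias. Power is 72–87% unadjusted and 94% adjusted.

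**The case against.** The strongest reply is that the plan already commits to a covariate model and collects the size data. That stands. A reader might infer that no adjusted analysis of REE is planned; the Data Analysis text does not support this. What remains is that the GLM is unspecified for REE and unranked, while the powered comparison is the unadjusted one.

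Several other limits also stand:

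- **Only one contrast is affected by design.** A reader might infer that both Aim 2 contrasts are confounded. Healthy obese and insulin-resistant children share the same BMI criterion, and the documents report no size difference between them.
- **Per-kilogram REE.** A reader might infer that dividing by weight could manufacture a deficit. No passage proposes dividing, and the Aim 4 wording points to whole-body REE, so that scenario is speculative and carries no weight here.
- **Confounding is not ignored throughout.** Of the depression scale the protocol says "This scale will be used to account for depression as a confounding factor that could affect oxidative and bioenergetics parameters". It would be wrong to infer that nothing else was considered: puberty is discussed at length as something that could alter results, and diet is recorded because it influences fat oxidation. Body size in relation to REE is what is left out.
- **Early-stage study.** No primary outcome is declared, and the results are meant to show whether a large study is warranted. This lowers the stakes. Even so, a contrast whose sign can be set by body size is a poor guide to that decision.
- **FFM adjustment changes the question** to whether REE is low for the child's lean tissue. Where overlap is small, the answer leans on the linear slope. This is a real cost of the fix, not a reason to let the unadjusted contrast decide.

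**Conclusion.** The point holds for one contrast and one outcome. For whole-body REE, the unadjusted insulin-resistant versus lean comparison is confounded with body size because the groups are selected on BMI, and the bias tends to mask or reverse the predicted decrease. That conclusion needs only the group definitions and REE that rises with size.

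The size of the effect rests entirely on assumed inputs and the ranges are wide. Under the main assumptions, a 100 kcal/day deficit is declared 0–33% of the time unadjusted against 72–91% FFM-adjusted with three groups, or 0–25% against 68–88% with four. Wrong-direction significance at an 8 kg gap is 5–72% or 3–64%. The adjusted figures assume that the linear model is correct and FFM is measured without error.

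This should be fixed before analysis. It is a matter of specifying and ranking the adjusted model, not of a missing one.

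**What to change.** In Data Analysis, for REE under Aim 2:

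- Analyse REE in kcal/day.
- Make the promised GLM the deciding analysis, with group, bioimpedance FFM, age and sex, and Tukey-adjusted comparisons of adjusted means in the three groups used in the Sample Size Justification. Report the unadjusted ANOVA as supportive.
- State that the fourth group in the ANOVA paragraph (metformin, up to 17 years 5 months) is not part of this comparison.
- Report how far lean and obese children overlap in FFM.
- Repeat the model with weight in place of FFM, both as a sensitivity analysis and where impedance is missing, since impedance is worded as optional.
- Adjust REE correlations with bioenergetic and redox measures for FFM, age and sex. Show them with and without group, because adjusting for group may remove association that Aim 2 asks about.

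**Cost.** No new measurements, and three degrees of freedom for the covariates. The stated power does not describe the adjusted lean contrast. In simulation under the main assumptions, the model with FFM, age and sex had 57–90% power, and 57–59% at an 8 kg gap, where it depends most on the linear slope. Impedance error leaves some bias: with 1 kg random error and a slope of 20, a true −100 was estimated as about −93, −89 and −81 at gaps of 3, 5 and 8 kg, with power 81%, 66% and 40%. The gain is less bias, not more precision.

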- Age 5-9 years and Tanner stage as reported by parent no greater than stage 1 OR Age 5 years - 17 years 5 months, diagnosed with type 2 diabetes mellitus or insulin resistance and prescribed metformin (not yet taking)
- Either healthy lean ($BMI \geq 5^{\text{th}}$ percentile and $< 85^{\text{th}}$ percentile for age/sex) or obese ($BMI \geq 95^{\text{th}}$ percentile for age/sex)
- For those with $BMI \geq 95^{\text{th}}$ percentile for age/sex, parental verbal confirmation will be obtained that the child had a history of $BMI \geq 95^{\text{th}}$ percentile for age/sex for at least six months prior to study enrollment

Exclusion criteria:

- Genetic or physical conditions impacting mobility over past year as determined by the PI
- Having known chronic illnesses/disorders that may independently affect study outcome measures: type 1 diabetes mellitus, neurologic (e.g. epilepsy), developmental (developmental delay, autism spectrum disorder), endocrine (thyroid, Cushing's), hepatic, autoimmune, cardiac and renal disorders. Also, chronic lung disorders except well controlled asthma that does not require permanent use of inhaled/oral steroids
- Taking any of the following medications that can affect study outcome: antipsychotics, thyroid hormone replacement therapy, inhaled/oral steroids, insulin, anabolic drugs (growth hormone replacement therapy and oxandrolone) and stimulants
- Taking metformin prescribed as part of their clinical care at the time of enrollment (may begin metformin therapy prescribed as part of their clinical care while enrolled in the study)
- $BMI < 5^{\text{th}}$ percentile for age/sex (classified as underweight based on CDC growth charts)
- Subjects determined ineligible by the PI.

Risks and Benefits

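### The four-group ANOVA adds an older, possibly pubertal group that Aims 1–2 and their power calculation leave out, so the overall F test and every contrast with that group are confounded by age and puberty

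*Combined protocol and SAP*

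**What the plan says.** - **Analysis.** Data Analysis (Statistical and Power Analyses) specifies a one-factor ANOVA to "compare mean outcome of interest across the groups of children (healthy lean, healthy obese, obese insulin resistant and obese T2D"). Tukey-Kramer pairwise tests follow at a 5% family-wise error rate. The fallback is Kruskal-Wallis with Bonferroni-corrected Wilcoxon tests. On adjustment it says only: "Generalized linear model (GLM) will also be used to incorporate important covariates and effect modifiers into the analysis".
- **Aims.** Specific Aim 2 asks whether REE and FAO are "decreased in obese insulin resistant as compared to lean and obese insulin sensitive children". Aim 1 has the same three-group form.
- **Sample size.** The justification for Aims 1 and 2 uses a one-factor ANOVA on 110 children: 70 obese insulin resistant, 20 healthy obese and 20 healthy lean.
- **Fourth group.** Study Population defines it as "children with T2D or insulin resistant who have been newly prescribed metformin therapy as part of their clinical care", n = 20.
- **Eligibility.** One inclusion branch is age 5–9 with parent-reported Tanner stage no higher than 1. The other is "Age 5 years - 17 years 5 months, diagnosed with type 2 diabetes mellitus or insulin resistance and prescribed metformin", with no Tanner limit.
- **Population as described for analysis.** "175 pre-pubertal children ages 5-9 years old will be recruited for this study".
- **Design.** Item 1 of Study Design and Procedures is "An observational cross sectional bioenergetic and metabolic analysis of several groups of children including lean, obese, and T2D".
- **Puberty.** The Tanner assessment procedure states: "At the beginning stages of puberty, insulin levels rise dramatically showing insulin resistance". It adds that wrong conclusions could follow if a child has entered puberty.

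**The concern.** The analysis has four groups, whereas the aims and the power calculation have three. The extra group differs from the others by eligibility rule in age and pubertal stage as well as in metabolic status. A significant overall F, or a significant contrast with the fourth group, could come from age or puberty alone and be reported as a metabolic difference. The protocol itself names puberty as a route to that error.

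The label adds a second problem. No recruited group consists only of children with T2D, so the text does not settle whether the fourth ANOVA level is the whole new-metformin group or a T2D subset of unstated size.

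A smaller cost falls on the comparisons the study was designed for. Insulin resistant v lean and insulin resistant v healthy obese are now judged within a family of six comparisons instead of three.

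**Working it through.** **1. Inputs from the documents.** Completers are 20 (lean), 20 (healthy obese), 70 (insulin resistant) and 20 (new metformin), total 130; α = 0.05. The size of any age or puberty effect on the outcomes is not given, so a shift s of 0.25 to 1.0 SD is assumed, with the other three groups equal and a common SD.

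**2. The plan's own figure.** With noncentrality λ = N·f² and degrees of freedom k−1 and N−k, the stated inputs (k = 3, N = 110, 80% power) give a detectable f of 0.300. The plan states 0.33, at which power would be 87%. The stated figure does not reproduce, but the difference is conservative and nothing below depends on it.

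**3. Is overall sensitivity lost with four groups?** For k = 4, N = 130, detectable f is 0.294, and power at f = 0.33 is 89%. Sensitivity of the overall test is not worse.

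**4. Confounding of the overall F.** If only the fourth group (size m) is shifted by s, then λ = s²·m·110/(110 + m). For m = 20 this is s² × 2200/130 = 16.92·s².

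| Shift s (SD) | λ | Probability that F rejects |
|---|---|---|
| 0 | 0 | 5% |
| 0.25 | 1.06 | 12% |
| 0.50 | 4.23 | 37% |
| 0.75 | 9.52 | 72% |
| 1.00 | 16.92 | 94% |

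If the fourth level means only the T2D children, m is unknown. At s = 0.5, m = 5, 10 or 15 gives λ = 1.20, 2.29 or 3.30 and rejection in 13%, 21% or 29%.

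**5. Where the false signals fall.** In a simulation of 40,000 studies with m = 20, at least one Tukey contrast involving the fourth group was significant in 3%, 10%, 36%, 74% and 94% of studies for s = 0, 0.25, 0.5, 0.75 and 1.0. At least one contrast among the other three groups was significant in about 2.7% throughout. The bias does not reach the Aims 1–2 contrasts.

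**6. Multiplicity cost to the Aims 1–2 contrasts.** The Tukey-Kramer critical t is the 95% studentized range quantile divided by √2. For 70 v 20, the standard error in SD units is √(1/70 + 1/20) = 0.2535, so d = 0.8 gives noncentrality 0.8/0.2535 = 3.16.

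| | Three groups (107 df) | Four groups (126 df) |
|---|---|---|
| Critical t | 2.38 | 2.60 |
| Detectable d, 70 v 20, 80% power | 0.82 | 0.875 |
| Power at d = 0.8 (assumed) | 78% | 71% |
| Bonferroni α per test in the fallback | 0.05/3 = 0.0167 | 0.05/6 = 0.0083 |

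With 5 to 15 children in the fourth group, the critical t is 2.61.

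**7. Can the GLM repair it?** It names no covariates. By eligibility, ages 10 to 17 and Tanner stage 2 or above occur only in the fourth group, apart from parental misreport. Outside whatever overlap exists at ages 5–9 and Tanner 1, an adjusted comparison is extrapolation.

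**The case against.** The strongest reply is that the confounded tests are ones no aim relies on. Aims 1–2 need contrasts among the first three groups, which are unbiased. Aim 4, which concerns the metformin group, uses a within-child paired test. Tukey-Kramer shows which groups differ, so a significant F need not mislead about the first three. The cross-sectional design item lists T2D, so a four-group comparison has support in the protocol. The Tanner procedure says physician staging may be used in analysing results, which suggests that puberty would be considered. The shift range is assumed, and fourth-group children aged 5–9 at Tanner 1 would dilute it. Controlling error over every group compared is legitimate, and moving three comparisons out of the family recovers power partly by doing so. The study is also presented as a guide to whether a larger one is warranted.

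Much of this stands, and it limits the size of the problem. It does not remove it. The ANOVA as written is unadjusted, and its overall F and three of its six contrasts would be reported. The Tanner remark does not put Tanner stage into the model, does not mention age and cannot create overlap. The design item does not reconcile a four-group test with three-group aims and a three-group power calculation. The lost inference on the fourth group is a real cost, but Aims 1–2 do not ask for it.

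**Conclusion.** The concern holds, and the analysis is wrong as written. Following the plan produces an overall F test and three fourth-group contrasts that cannot separate metabolic status from age and puberty. The rejection rates of 12% to 94% are illustrations. They rest on the assumed shifts, equal means in the other groups, a common SD and 20 children in the fourth group; the true size depends on the ages and Tanner stages enrolled, which the documents do not give. The Aims 1–2 contrasts are not biased and overall sensitivity is not reduced; their cost is the modest loss of pairwise power shown above. The description of all 175 children as pre-pubertal and aged 5–9 contradicts the Study Population section and the inclusion criteria whatever the effect size. This should be fixed before analysis, but it does not undermine the core comparisons.

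**What to change.** - State that the primary Aims 1–2 analysis is the three-group ANOVA with Tukey-Kramer (healthy lean, healthy obese, obese insulin resistant; n = 110), and use the same three groups in the Kruskal-Wallis and Wilcoxon fallback. This matches the power calculation.
- Because the design section lists T2D in the cross-sectional part, keep the fourth-group comparison as a separately labelled secondary or descriptive analysis. Name age and Tanner stage as covariates, say that adjustment outside the overlap is extrapolation, and add a subset at ages 5–9 and Tanner 1 where numbers allow.
- Rename the fourth group as new metformin prescription (T2D or insulin resistance), or state exactly which children the T2D label means.
- Reconcile the sentence on 175 pre-pubertal children, and the remark in the Tanner procedure that the criteria keep out children in puberty, with the Study Population section and the inclusion criteria.

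The cost is wording in the analysis section and those two sentences. No new data are needed, since date of birth and Tanner stage are already collected. The downside is that there is no primary inferential comparison with the fourth group, and its comparisons leave the 5% family. The ages 5–9, Tanner 1 subset may also be small.
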